12.2. Blinding

12.2.1. For Clinical Phase

This trial is planned as open-labelled in clinical phase. Investigator will have the information of which subject will take which **tablet** [Test or Reference] in study. Also, the subjects will have the information about the **tablets** which will be administered in the study period.

12.2.2. For Analytical Phase

This trial is planned as fully blinded in analytical phase. The exact list will be in a sealed envelope and this envelope will be opened at Novagenix in a “Project Evaluation Meeting” when all laboratory analyses are over. Once the sealed envelope is opened, no more reanalyse or data change/exclusion will be allowed.

12.3. Dosage, Duration of Treatment

All volunteers will receive in each period once daily either test drug or reference drug as 200 mg lopinavir and 50 mg ritonavir (*in Period II and Period IV, the subjects will be administered by the other drug that they will not administered in the Period I and*

Period III). The instructions for intake of the study medication are given in section 13.5 and separately on a sheet to be kept in the room where administration takes place.

12.4. Compliance

On each day of administration and/or sampling the identity of the volunteer will be confirmed by checking the Identity Card. Administration of the study medication will be performed by the investigator(s) and nurse(s) and supervised by a second medical professional to ensure the correctness of drug administration. Also, a personnel (monitor) from **ALPAN Farma** will attend during this procedure. The administration of the study medication is to be followed by a mouth check, to be documented in the CRF and certified by the Investigator.

12.5. Handling and Drug Accountability

The study medication will be packed and labelled according to GMP requirements. The study medication will be provided by the Sponsor together with certificates of analysis in a sufficient quantity for the needs of the whole trial. The Sponsor is responsible for keeping an appropriate amount of each study medication at the facility or at **ALPAN Farma** in order to allow repeated pharmaceutical analysis.

The investigator will confirm receipt of study medication in writing, including all follow-up supplies. The investigator will administer the study medication only to volunteers included in the study by following the procedures set out in the study protocol, as given in chapter 13.2. All drug supplies (test and reference medication, unused medication, empty blisters) which have not been used have to be returned to **ALPAN Farma or World Medicine İlaç San. ve Tic. A.Ş.** after completion of the study. It is not allowed to use the study medication for any other purpose.

12.6. Concomitant Medication

Concomitant medication is generally not allowed for the duration of the trial. If this is considered necessary for the volunteer's welfare, it may be given at the decision of the investigator. The volunteers have to inform the investigator about any intake of other drugs in the course of the trial. *If necessary, for the treatment of ordinary pain (e.g. headache), some analgesics (paracetamol etc.) which have no drug interaction with study products, may be given by investigator.* Any intake of concomitant medication has to be documented in the Case Report Form (“concomitant medication form”, “adverse event form” and “drop-out sheet”) specifying the substance, dose, time and reason for use of concomitant medication and may be regarded as an exclusion criterion.

12.7. Rescue Medication

No specific rescue medication is planned for the present trial since it is not a therapeutic trial and the safety / tolerability profiles of the administered drug substance are well known.

12.8. Storage of Study Medication

The investigator will be responsible for proper storage of the investigational products. All drug supplies must be stored in original package to protect from light and moisture in a dry place at room temperature below 25°C, and separately from normal hospital/practice stocks, locked and only accessible for authorized personnel, in accordance with the manufacturer's instructions. All supplies must be accounted for at the end of the study. A drug inventory form is to be filled in for this purpose.

13. STUDY PROCEDURE

13.1. General Procedure

Volunteers eligible for inclusion within the age limits as defined in section 11.1 will be asked for informed consent as described in **Appendix 7** due to the Covid-19 outbreak precautions and as described in section 20.3 and will be thereafter screened with respect to inclusion and exclusion criteria.

The initial examination will be carried out on the day of the beginning of the isolation as described in **Appendix 7**. The standard clinical screening includes demographic data, brief anamnestic data (medical history with information about relevant previous diseases of all body systems), physical examination, determination of body temperature, weight and height, standard ECG (12 lead), measurements of blood pressure (BP) and pulse rate (PR) after 5 minutes supine rest.

The standard laboratory screening includes serum levels of “CBC, glucose, urea, uric acid, creatinine, *estimated GFR (eGFR)*, total bilirubin, sodium, potassium, calcium, chloride, SGOT (AST), SGPT (ALT), GGT, alkaline phosphatase, total protein and urinalysis”. The blood specimen (20 mL* for entry and 12 mL for final) for the safety laboratory will be taken under fasting conditions. Total blood sampling for both laboratory examinations (entry and final) will be 32 mL. The volunteers will also be checked for presence of HBsAg, HCV-Ab and HIV-Ab in serum and **Covid-19 Rapid Test and Covid-19 PCR test**.

Clinical laboratory tests will be performed using the auto analyser at a contracted and certified laboratory (**GAMA Tip Merkezi-G.Antep**). **Covid-19 PCR test will be performed at “Gaziantep University Şahinbey Research Hospital, Molecular Genetic Diagnosis, Hematology and Tissue Typing Laboratory”**.

** At entry examination the blood sample amount will be 20 mL and 8 mL sample of 20 mL sample will be divided into tubes and one of this tube will be used for the anti-coagulant validation purpose during the analytical validation process. This plasma sample will send to Novagenix with master and back-up samples.*

The following parameters are determined in urine (30 mL): pH, protein, glucose (semi quantitatively by means of strip test), ketones, blood, leukocytes, bilirubin, nitrites. If the strip test for any urine parameter is positive, a microscopic examination of the sediment has to be done.

At screening volunteers will be requested to provide a urine sample for a drug screen which will include “*amphetamines, cannabinoids, benzodiazepines, cocaine, opioids and barbiturates*” and for an alcohol breath test. All laboratory tests will be carried out in a certified local laboratory. A list of the normal ranges and units of measurement of the laboratory parameters to be determined during the study and the certificate of the laboratory will be provided by the investigator before the start of the study. The reference ranges and the results of the individual laboratory examination will be documented in each CRF. The investigator will be provided with a print-out or authorized copy of the original laboratory values.

If in the course of initial screening any clearly pathological value (laboratory value outside reference range, clinically relevant or significant) is observed, this finding will be regarded as an exclusion criterion.

Laboratory values outside the normal range will be judged by the investigator in a written form in the CRF. Single laboratory values outside the normal range will generally not be regarded as an exclusion criterion provided that:

- a) they are not accompanied by clinical symptoms,
- b) the context of related laboratory values gives no indication of a pathological process and
- c) the investigator regards them as clinically irrelevant in written form in the CRF.

If Covid-19 PCR test result is positive, the volunteer(s) will be transfer to Gaziantep University Şahinbey Research Hospital, Emergency Department* under appropriate conditions immediately. This finding will be regarded as an exclusion criterion.

***Contact Physician: [name]. [name]**

Gaziantep University Şahinbey Research Hospital,
Emergency Department
GSM: [name]

The test and reference product will be administered under **fasting** conditions each in a randomised manner in **four period** with at least **48 hours wash-out** period. Volunteers will be treated under hospitalization conditions in study period and will be hospitalised at the Clinical Facility (FARMAGEN-Good Clinical Practice and Research Center) from the evening of Day 0 (hospitalization) normally until taking the last blood sample in 4th period and carried out the post-study and final examination to ensure subjects' safety as well as standardised trial conditions during profiling days (e.g. in view of food and fluid intake, diet, **fasting** conditions, drug administration, clinical and other procedures). Adverse events will be monitored throughout the study. The medical care of the volunteers will be guaranteed by the presence or stand-by of the investigator or one of the co-investigators throughout the clinical phase of this trial.

The volunteers will come to the clinic **from isolation, described at Appendix 7**, at approximately **18:00** on the day before the treatment (Day 0) of study and will remain there for **8 days**. A measurement of body temperature will be performed once a day in the mornings during the study period. They will not be allowed to drink water between 1 h before to 1 h after administration, except while dosing (the total intake of water on the days of dosing will be maximum 1.5 L). The investigator will check on each volunteer's wellbeing prior to their discharge from the clinic. If necessary, some volunteers will remain at the clinic until any adverse events have resolved. All volunteers will be subjected to a post-study examination and final examination and laboratory tests on the day of last sampling in **fourth period**.

For each volunteer being withdrawn from the study prior to regular termination of the individual study period, due to whatever reason, a complete final examination has to be performed at the time of withdrawal as far as possible with regard to the volunteer's health conditions and as far as necessary with regard to safety aspects. **All taken plasma samples will be analysed. But will not be included to statistical calculations.**

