10. DESIGN

In this open-label, randomised, single-dose, two-sequence, two treatment, four-period, full-replicated, cross-over study, **30 healthy** male subjects (intention to treat population) will receive one single oral dose of **200 mg lopinavir and 50 mg ritonavir [either one tablet of the test drug or one tablet of the reference drug according to the randomisation table]** under fasting conditions, according to a sequence determined by randomisation [in Period II and Period IV, the subjects will be administered by the other drug that they will not administered in the Period I and Period III].

Data of the subjects who have completed the study according to the Clinical Study Protocol will be used for analytical, pharmacokinetic and statistical evaluation.

Test Drug: “Orvical 200 mg/50 mg Film Tablet” is manufactured by World Medicine İlaç San. ve Tic. A.Ş., Turkey and is will be licensed by World Medicine İlaç San. ve Tic. A.Ş., Turkey.

Reference Drug: “Kaletra 200 mg/50 mg Film Kaplı Tablet” is manufactured by AbbVie Deutschland GmbH & Co. Germany and is licensed by AbbVie Tıbbi İlaçlar Sanayi ve Ticaret Limited Şirketi-İstanbul, Turkey

In study period, the subjects will be admitted to the FARMAGEN Clinical Unit in the evening (18:00) prior to morning of the administration of medication after **screening and isolation period as described in Appendix 7.**

Volunteers will be confined to the clinical unit and dosing will occur under conditions of hospitalization. Medications will be orally administered at approximately at 8:00 (t=0) after an overnight fasting (at least 10 hours in fasting). The lunch will be 4 hours post dosing and the dinner will be 10 hours post dosing. Blood sampling for the determination of **lopinavir and ritonavir** plasma concentrations will be drawn at specified time points. After taking the last blood sample and carried out the post-study examination, the subjects will be allowed to leave the clinic.

An overview of the study procedures is given in the Study Flow Chart provided in section 6.

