14.1. Withdrawal of Volunteers

Volunteers may be withdrawn for the following reasons:

- at their own request with or without giving reasons,
- at the discretion of the investigator for reasons of medical prudence.

In either event, the Sponsor will be immediately notified and the date and reasons for the withdrawal will be clearly stated in the volunteer's CRF.

Volunteers must be withdrawn under the following circumstances:

- if personal circumstances suggest that the visits required by the protocol cannot be guaranteed any longer,
- if adverse events (including intercurrent illnesses) develop, which rule out continuation of the study medication, or, due to impaired validity of the results, make it appear inadvisable to further participate in the study,
- **If Covid-19 PCR test result is positive, the volunteer(s) will be dropped out from study.**
- if subjects who have intaked or administrated of any prescribed systemic or topical medication (including OTC medication) within **2 weeks** of the start of the study (*except singles doses of analgesics which have no drug interaction with study products*) given in case of an adverse event (e.g. headache) during the study,
- if circumstances defined as exclusion criteria are registered,
- if administration of any drug is necessary, which is not permitted according to the exclusion criteria (see section 11.2), independently of its necessity due to the occurrence of adverse events (including intercurrent illnesses) or of its use due to other reasons,
- if vomiting occurs at or before 2 times median t_{max} .
- if diarrhea exists during screening and /or medication day.

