14.4. Drop-out Samples

All drop-out samples which will be sent by the clinic will be analysed and results will be given in the Final Study Report.

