18. PHARMACOKINETIC EVALUATION

Pharmacokinetic parameters of **lopinavir and ritonavir** will be determined using non-compartmental methods from measured plasma concentrations.

For each treatment (**Test Drug** or **Reference Drug**) and each volunteer participating completely in this **single-dose, four-period, full-replicated, cross-over study** the following pharmacokinetic parameters will be calculated:

Primary pharmacokinetic parameters:

C_{max}: Maximum observed plasma concentration

AUC_{0-last}: Area under the plasma concentration-time curve from zero to the last measurable concentration, calculated by the linear log trapezoidal rule.

Secondary pharmacokinetic parameters:

AUC_{0-∞}: Area under the plasma concentration-time curve, calculated by extrapolation to infinity.

t_{max}: Time to maximum observed plasma concentration

t_{1/2}: Terminal half-life

Additional pharmacokinetic parameters:

MRT: Mean residence time

λ_z: Terminal rate constant.

For pharmacokinetic calculations, the program package **Phoenix WinNonlin (Version 8.1, Certara L.P.)** or above will be employed. Phoenix WinNonlin will also be used to generate concentration/time plots.

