19. STATISTICAL PROCEDURES

The statistical analysis of the pharmacokinetic data described in this section corresponds with provisions given by the CPMP guideline CPMP/EWP/QWP/1401/98 Rev. 1 dated 20 January 2010.

Statistical analysis will be performed as a valid case analysis including all volunteers in which no major protocol deviations occurred and all primary target variables are available for measurement.

If a volunteer is to be excluded from evaluation, this decision has to be justified in the Final Study Report. Statistical analysis will be performed by means of the program **Phoenix WinNonlin (Version 8.1, Certara L.P.)** or above.

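### Completers-only rule discards test and reference profiles fully sampled before a later, unrelated withdrawal event; a small, avoidable loss of precision

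*Combined protocol and SAP*

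**What the plan says.** Four sections of the combined protocol and SAP define who is analysed, and they agree.

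- Section 10 (Design): "Data of the subjects who have completed the study according to the Clinical Study Protocol will be used for analytical, pharmacokinetic and statistical evaluation".
- Section 13.1 (General Procedure), on volunteers withdrawn early for any reason: "All taken plasma samples will be analysed. But will not be included to statistical calculations".
- Section 18 (Pharmacokinetic Evaluation) calculates parameters for "each volunteer participating completely in this" four-period study.
- Section 19 (Statistical Procedures) analyses "all volunteers in which no major protocol deviations occurred and all primary target variables are available for measurement".

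Section 14.4 has the withdrawn volunteers' samples assayed and listed: "All drop-out samples which will be sent by the clinic will be analysed and results will be given in the Final Study Report". Section 14.1 contains withdrawal triggers that can arise in one period only, among them "if vomiting occurs at or before 2 times median" tmax, "if diarrhea exists during screening and /or medication day", and leaving "at their own request with or without giving reasons". Section 14.2 rules out replacement, and section 19.2 states no drop-out allowance for the 30 volunteers. The exclusion criteria in 19.1.3 only remove data, and the blinded meeting in 22.2 concerns protocol violations. Neither brings back periods completed before a withdrawal.

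**The concern.** In a two-treatment replicate design, half-way through the study each volunteer has already supplied a within-subject comparison of test and reference. If he then vomits in Period III, the Period III profile is compromised, but the Period I and II profiles, sampled to 36 h and finished, are not. The plan nevertheless removes all of them.

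What is at stake is precision. Valid data that will be assayed anyway do not reach the confidence interval, in a study of exactly 30 without replacement. AUC is the more exposed variable, because its limits stay at 80.00-125.00% whatever the variability. An RTRT volunteer who withdraws in Period IV also has both of his reference profiles dropped from the estimate of s_WR.

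**Working it through.** **Inputs.** TRTR/RTRT (13.3, 19.3); 30 volunteers, CV 30-35%, ratio 0.90-1.10 (19.2); 21 samples per period (13.7); ANOVA with sequence, subject within sequence, period and treatment, and a 90% CI (19.1.3); AUC limits 80.00-125.00%. The withdrawal count is not in the documents and is assumed here.

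**Baseline with all 30.** Standard error = s_w·√(1/30), with s_w = √ln(1+CV²) and 3·30−4 = 86 degrees of freedom. AUC power at CV 35% is 59.4%, 86.2%, 94.5% and 65.5% at ratios 0.90, 0.95, 1.00 and 1.10. The plan's 80% is therefore exceeded at 0.95 and 1.00 but not reached at 0.90 or 1.10. That shortfall exists with nobody withdrawn and is a separate sample-size matter.

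**What one withdrawal costs.** With fixed subject effects and period terms ignored, a volunteer's information on test minus reference is proportional to nT·nR/(nT+nR).

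| Withdrawn in | Profiles finished | Information | Kept now | Samples assayed but unused |
|---|---|---|---|---|
| Period I | 0 | 0 | 0 | 0 |
| Period II | 1 | 0 | 0 | 21 (no T−R information) |
| Period III | 2 | 1·1/2 = 0.50 | 0 | 42 |
| Period IV | 3 | 2·1/3 = 0.67 | 0 | 63 |
| Completes | 4 | 2·2/4 = 1.00 | 1.00 | none |

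**Hand check of the CI width.** With withdrawals spread evenly over periods, the average loss per withdrawal is 1 now. With profiles retained it is (1 + 1 + 0.50 + 0.33)/4 = 0.71. For five withdrawals, √(30/25) = 1.095 now and √(30/(30 − 5·0.71)) = √(30/26.45) = 1.065 with retention.

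**Full model** (subject, period and treatment effects, simulated withdrawal patterns). This adds sequence imbalance and lost degrees of freedom, so the figures are slightly larger:

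| Withdrawals | CI wider, now | CI wider, retained | AUC power, CV 35%, ratio 0.95 | AUC power, CV 35%, ratio 0.90 |
|---|---|---|---|---|
| 1 | 1.8% | 1.3% | 85.0 → 85.3% | 58.1 → 58.4% |
| 3 | 5.7% | 3.9% | 82.4 → 83.6% | 55.4 → 56.6% |
| 5 | 10.2% | 7.0% | 79.3 → 81.5% | 52.5 → 54.6% |

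**As a rate per dosing day.** At p = 1%, 2.5% or 5%, expected withdrawals are 30 − 30(1−p)^4 = 1.2, 2.9 and 5.6. Those with usable earlier profiles are 30[p(1−p)² + p(1−p)³] = 0.6, 1.4 and 2.6. Across ratios 0.90, 0.95, 1.00 and 1.10 the AUC power gain is 0.3-0.5, 1.0-1.3 and 2.3-2.7 points at CV 35%, and 0.1-0.5, 0.4-1.3 and 1.2-2.5 points at CV 30%.

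**Cmax and s_WR.** For Cmax with widened limits (CV 35%, ratio 0.90, 6000 simulated trials per case), power is 77.3% with all 30. At the three rates it moves from 75.8 to 76.6%, 73.2 to 74.7% and 68.6 to 71.2%. The standard error of one figure near 76% is √(0.76·0.24/6000) = 0.55 points, so about 0.8 points for a difference between independent runs; the first change is within simulation noise. Mean degrees of freedom for s_WR rise only from 26.9 to 27.0, 25.1 to 25.4 and 22.4 to 23.0.

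**The case against.** The strongest reply is that a completers-only set is a legitimate choice, stated in advance and consistently in four sections, and that the gain is small. Both parts are true. At one withdrawal the benefit is a fraction of a power point, and gains above two points need about five or more of 30 healthy, confined men to withdraw. Withdrawals in Periods I and II gain nothing. What remains is that the loss has no offsetting benefit when the earlier profiles are sound.

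A second reply is sound and shapes the remedy. Some triggers in 14.1 reach backwards: a prohibited or enzyme-inducing drug, grapefruit, or an exclusion criterion that was present all along but found in Period III. Because lopinavir is cleared almost exclusively by CYP3A (7.3.3), such a finding can invalidate Periods I and II as well. Retention cannot be unconditional.

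A reader might also infer more than the documents support:

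- *That diarrhoea will cause many withdrawals.* Section 7.6 lists it as very common in general use; no rate is given for single doses in healthy men.
- *That Covid-19 testing will remove volunteers in mid-study.* The flow chart schedules volunteer PCR at screening, Day 0 and the final examination. The daily tests in 13.2 are for clinic staff. Appendix 7 is not in the text available.
- *That samples or safety data are lost.* The concentrations are assayed and reported under 14.4, and the rule concerns only the statistical calculations.

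**Conclusion.** The point holds as a minor loss of precision. The four sections do exclude every profile of a withdrawn volunteer, including complete test and reference profiles that a later event leaves untouched. The size depends on an assumed number of withdrawals, spread evenly over the periods. For 1, 3 or 5, retention recovers roughly 30% of the added CI width (for five, (10.2 − 7.0)/10.2 = 31%). If nobody withdraws in Period III or IV, the gain is zero.

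Two stronger conclusions are not supported. The exclusion is not shown to bias the test/reference ratio, and none is claimed. Nor does it cause the AUC power of about 59% at CV 35% and ratio 0.90, which is present with all 30 retained.

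**What to change.** Leave the withdrawal rules in 14.1 as they are. In sections 10, 13.1, 18 and 19, state the following:

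1. Profiles fully sampled to 36 h before the withdrawal event stay in the ANOVA if the volunteer has at least one complete test and one complete reference profile. The period in which the event occurred is excluded.
2. Earlier profiles are not kept when the reason for withdrawal also affects those periods, for example a prohibited or enzyme-inducing drug, grapefruit, an exclusion criterion already present, or another major deviation under section 19.
3. The decision is made from recorded times and reasons and documented before the treatment envelope is opened (19.3), since no data change or exclusion is permitted afterwards.
4. A volunteer contributes to s_WR only with two complete reference profiles. Among those withdrawn, this means RTRT volunteers who leave in Period IV.
5. The completers-only analysis is reported as a sensitivity analysis.

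The cost is wording and one extra run. No visits, samples or assays are added, because 14.4 already has these samples analysed. The drawbacks are a slightly unbalanced ANOVA, in which the terms of 19.1.3 can still be fitted, different subject sets for the CI and s_WR, and a judgement under item 2 that the present rule does not need.
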